5.3 Pre-screening Assessments

Prior to their scheduled Screening and Baseline virtual visit, subjects will be asked to complete the following:

- Medical & concomitant medication history
- Demographic information
- The MFI
 - Following MFI completion, the participant's MFI score will be automatically calculated via the Citrus platform to determine eligibility. A subject is considered eligible if their baseline score is ≥ 10 on the dimension of general fatigue of the MFI and a score ≥ 3 for at least ten of the 20 questions of the MFI.

Note: If the participant is not eligible based on responses to the above items, a member of the study team will notify and screen fail the participant.

Property of Haleon- Confidential

May not be used, divulged, published or otherwise disclosed without the consent of Haleon

CCI [REDACTED] Abbreviated Clinical Protocol Template v1.0

5.4 Screening & Baseline: Virtual Visit 1

During the Screening and Baseline virtual visit, a trained member of the study team will verify the subject's identification (i.e. driver's license or government issued passport) on camera at the beginning of the visit. Should the subject elect not to show a form of identification or is unable to provide a valid identification at the beginning of the virtual visit, the visit may be rescheduled, or the subject may be considered a screen failure.

Following subject identification verification, the following visit procedures will be performed:

- Review self-reported medical and concomitant medication history
- Review inclusion/exclusion criteria
- Complete supplemental QoL questionnaire
- Provide instructions for the completion of the study questionnaire, daily diaries, and storage, preparation and administration of the study product
- Verify address for study product shipment
- Answer any questions the subject may have about the study

If the responses to all screening criteria are fulfilled, the subject will be considered enrolled. At enrollment, the following activities will occur:

- The subject will move forward to randomization into one of two study groups (on a 1:1 allocation) as follows: Group 1) Emergen-C Core Super Orange Powder or Group 2) Placebo.
 - Upon group allocation, subjects will be shipped the study product. Neither the subject or study team will be made aware which group arm the subject is allocated to.
 - Once the shipment is successfully received, the subject will confirm receipt via an online questionnaire directly entered into the EDC platform.
 - If unsuccessful (e.g. lost, damaged) study team will discuss with participant and arrange a new shipment if needed

Following the completion of the screening visit, and prior to Virtual Visit 2, subjects will be reminded each morning to consume the study product with 4-6 ounces of water at approximately the same time each day. Each evening, subjects will be prompted to complete an Electronic Diary (eDiary) consisting of one question to confirm the subject has consumed the study product.

5.5 Follow-up: Virtual Visits 2-4

Randomized subjects will participate in three follow-up visits conducted virtually with a trained study team member to review the following:

- Changes in concomitant medications and changes in health
- Subjects eDiary compliance & study product use
 - Subjects who are non-compliant with eDiary completion or study product use for greater than two consecutive days will receive a follow-up from a trained member of the study team re-educating them on study procedures.

Property of Haleon- Confidential

May not be used, divulged, published or otherwise disclosed without the consent of Haleon

CCI [REDACTED] Abbreviated Clinical Protocol Template v1.0

- Review any adverse events or safety events and pregnancies which may have occurred since the last virtual visit. Participants will also be able to report any (S)AEs and pregnancies to the study team between virtual visits via dedicated trial phone number.

5.6 On-going Daily eDiaries

The subject will receive links via text and email with instructions for completion of the study daily diaries. The subject will input their responses directly into the EDC platform. The daily eDiary consists of one question to confirm the subject has consumed the study product.

If subjects fail to complete or state “no” to the study product consumption survey for greater than 48-hours, the study team will contact the subject to re-educate on the study procedures and compliance.

5.7 On-going Assessments: Week 4, Week 8 & Week 12

On the first day of the visit window of week 4, week 8, and week 12, the subject will receive links via text and email with instructions for completion of the MFI and Supplementary QoL questionnaire. The subject will input their responses directly into the EDC platform. The subject will receive reminders to complete the MFI and the Supplementary QoL questionnaire. If the subject does not complete the MFI and the Supplementary QoL questionnaire within the 48-hour timeframe, a trained member of the study team will contact them via text, phone, or email. If the subject has not completed the MFI by the time of their scheduled virtual visit, they will be instructed to complete the MFI during the visit.

End of Treatment Period

Subjects will have the option to discontinue treatment at their discretion. The reasons for discontinuing treatment will be captured by a trained study team member and every effort will be made to capture reasons for discontinuation (i.e. follow up calls, letters, texts, or e-mails to the subjects, etc. Subjects will be informed that the study will end after week 12 and will be asked to fill out an exit survey.

6 STUDY ASSESSMENTS

Every effort should be made to ensure that protocol-required assessments and procedures are completed as described. However, it is anticipated that from time to time there may be circumstances outside the control of the investigator that may make it infeasible to complete an assessment. When a protocol-required assessment cannot be performed, the investigator (or designee) will document the reason for the missed assessment as a protocol deviation and any corrective and preventative actions that he or she has taken to ensure that required processes are adhered to as soon as possible. The Sponsor must be informed of any missed assessments.

6.1 Outcome Assessments

Assessments will be performed by delegated staff at the times, and in the order, defined in the Study Procedures section of this protocol.

The objective of the study is to evaluate the effectiveness of daily Emergen-C on QoL parameters. This includes self-reported outcomes from the Multidimensional Fatigue Inventory domains and supplemental QoL questions at baseline, week 4, week 8, and week 12.

Multidimensional Fatigue Inventory (MFI-20): The MFI (29) is a 20-item scale designed to evaluate five dimensions of fatigue: general fatigue (items 1, 5, 12, 16), physical fatigue (items 2, 8, 14, 20), reduced motivation (items 4, 9, 15, 18), reduced activity (items 3, 6, 10, 17), and mental fatigue (items 7, 11, 13, 19). Subjects will answer a series of questions indicating how they feel about each statement, lately. Items are scored 1–5, 1- indicating “yes, that is true” and 5- indicating “no, that is not true”, with higher total scores representing a worse outcome. For scoring, 10 positively phrased items reverse scored (this concerns the following items: 2, 5, 9, 10, 13, 14, 16, 17, 18, 19) while 10 negatively phrased items are scored at face value (this concerns the following items: 1, 3, 4, 6, 7, 8, 11, 12, 15, 20). For each of the 5 scales (general fatigue, physical fatigue, reduced activity, reduced motivation, and mental fatigue) a total score is calculated by summation of the scores of the individual items. Domain scores can range from the minimum of 4 to the maximum of 20, the higher the score the worse the level of fatigue outcome.

Supplemental QoL questions: Six additional questions will be asked to evaluate the effectiveness of the intervention on target outcomes. Subjects will answer a series of questions indicating how they feel about each statement, lately. Questions are scored 1–5, 1- indicating “yes, that is true” and 5- indicating “no, that is not true”, with higher total scores representing a worse outcome. Additional questions include:

- I feel more energized to look after my family and/or loved ones
- I feel more prepared for the future
- I feel resilient so I can be at my best each day
- I feel ready to cope with life’s challenges
- I feel relaxed
- I feel able to unwind

Subjects will be asked to report their health in the previous 4 weeks using four additional questions:

- In the last 4 weeks, how many days did you feel rundown, if any?
- In the last 4 weeks, how many days did you have to cancel plans or work because you were not feeling 100%, if any?
- In the last 4 weeks, how many days did you have cold and cough symptoms (for example: runny nose, blocked nose, sneezing, cough, sore throat), if any?
- In the last 4 weeks, how many days were you in bed sick, if any?

Exit survey question: Subjects will be asked to complete an exit survey following their completion of the study asking one question:

- Would you use your assigned supplement again?

Property of Haleon- Confidential

May not be used, divulged, published or otherwise disclosed without the consent of Haleon

CCI [REDACTED] Abbreviated Clinical Protocol Template v1.0

6.2 Safety and Other Assessments

The following safety assessments will be performed by appropriately trained staff/clinical examiners, at the times and in the order defined in the Study Procedures section of this protocol.

6.2.1 Pregnancy Testing

For Haleon studies in which no drug is utilized or studies of single use marketed products that are classified as a non-medicinal product in the market where the testing is occurring and there is no pregnancy warning on labeling, a pregnancy test will not be required.

Female subjects will provide verbal confirmation of pregnancy status at Screening (Visit 1) and will be asked to inform study staff immediately should this change at any point during the study. Female subjects who are pregnant or planning pregnancy during the study (self-reported) will not participate further in the study.

7 STUDY PRODUCTS

For the purposes of this study, per International Conference on Harmonization (ICH) guidelines, and Haleon policy, study intervention is defined as any investigational intervention(s), marketed product(s), placebo, or medical device(s) intended to be administered to a study participant according to the study protocol. This includes a product with a marketing authorization when used or assembled (formulated or packaged) in a way different from the approved form, or when used for an unapproved indication, or when used to gain further information about an approved use.

7.1 Study Product Supplies

Each subject will receive sufficient study product to cover usage during the treatment period of the study. The following study products will be supplied by the Sponsor's preferred vendor (Table 7-1). Study test product usage instructions are consistent with the commercially available pack instructions (excludes reference product). Subjects will not be required to return unused study products after treatment discontinuation or completion of week 12 study activities. However, subjects will be instructed to destroy unused study product after treatment discontinuation or completion of week 12 study activities.

Table 7-1 Investigational/Study Product Supplies

	Test Product	Reference Product
Product Name	Emergen-C Core Super Orange Powder	Placebo
Pack Design	Large carton containing 3 small cartons of 30 sachets each	Large carton containing 3 small cartons of 30 sachets each
Dispensing Details	One labeled carton (containing 3 cartons, with 30 sachets per carton) shipped to	One labeled carton (containing 3 cartons, with 30 sachets per carton) shipped to subject following baseline visit

Property of Haleon- Confidential

May not be used, divulged, published or otherwise disclosed without the consent of Haleon

CCI [REDACTED] Abbreviated Clinical Protocol Template v1.0

	subject following baseline visit	
Haleon formula codes:	CCI	CCI
Dose	As per label instructions: Subjects will consume one sachet stirred in 4-6 ounces of water once per day in the morning at approximately the same time each day	As per label instructions: Subjects will consume one sachet stirred in 4-6 ounces of water once per day in the morning at approximately the same time each day
Route of Administration	Oral	Oral
Usage Instructions	As per directions stated on the label	As per directions stated on the label
Return Requirements	All unused study products will be destroyed/disposed of.	All unused study products will be destroyed/disposed of.

7.2 Product Supplies, Product Storage, Accountability, Returns and Destruction

All study products supplied are for use only in this clinical study and should not be used for any other purpose. Guidance will be provided to the Sponsor's preferred vendor for the receipt, storage and management of products for the duration of the trial by Haleon Clinical Supplies and with further instructions included with the shipping documentation.

CCI preferred vendor should ensure that the room or area set aside for storage is able to maintain the correct temperature (room temperature) to meet the product label storage conditions, is sufficient to store all products and is secure and access controlled.

Any temperature excursions or discrepancies whilst study products are stored at site require the affected products to be quarantined and this must be communicated immediately to the Sponsor who will provide documentation to approve further usage. Use of any of the affected product(s) prior to sponsor approval will be considered a protocol deviation.

Study products are to be dispensed only to subjects enrolled in the study in accordance with the protocol, by designated investigator staff. Enrolled/randomized subjects will be informed on product usage and storage and what to do in the event of product loss when the products are first dispensed.

All study products will be accounted for using the investigational/study product accountability form/record. CCI preferred vendor is responsible for study product accountability,

Property of Haleon- Confidential

May not be used, divulged, published or otherwise disclosed without the consent of Haleon

CCI Abbreviated Clinical Protocol Template v1.0

reconciliation, and record maintenance. Unused study products will not be returned or destroyed.

7.3 Blinding and Randomization

Qualifying subjects will be centrally randomized into one of two study groups using a randomization list provided by Haleon Clinical Supplies. Before the study is initiated, training and directions for the randomization will be provided to the investigator study team. Study products will be dispensed in sequential order as per the randomization schedule. CCI [REDACTED] will submit a list of subject ID numbers and corresponding kit codes to the Vendor each day for study product shipment. Only subjects who meet the study inclusion criteria will be randomized to a study product.

This study is described as double-blind (i.e., the clinical examiner and study participants will be blinded to the study product each subject receives). Additionally, investigator staff involved in the clinical or safety assessments, study statistician(s), data management staff, other employees of the sponsor (including the sponsor's Clinical Research Scientist (CRS)) and vendors acting on behalf of the sponsor who may influence study outcomes, will also be blinded to treatment allocation.

To maintain the blind throughout the study:

- Subjects will see and use only one of the two study products during the study. They will be instructed not to discuss the appearance, usage, or perceived performance of their allocated study product with staff involved in clinical assessments or with other study subjects.
- The study product will be provided to the CCI [REDACTED] preferred vendor in unmarked cartons masking their identity and obscure any branding on the commercial product with a study label affixed. Both study products (treatment and placebo) are packaged in individual, unmarked, identical foil sachets.
- The study product will be supplied in individual packs (cartons); each large carton will contain three smaller cartons, each containing 30 sachets of study product (90 sachets total). Each subject will receive one large carton, marked with a kit number containing only their randomized study product; product codes will not be used.

7.4 Breaking the Blind

In case of an emergency, the investigator has the sole responsibility for determining if unblinding of a subject's product assignment is warranted. Subject safety must always be the first consideration in making such a determination. If the investigator decides that unblinding is warranted, the investigator should make every effort to contact the sponsor prior to unblinding a subject's product assignment unless this could delay emergency treatment of the subject.

If a subject's study product assignment is unblinded, the sponsor must be notified within 24 hours after breaking the blind. The date and reason that the blind was broken must be recorded in the source documentation and case report form, as applicable.

Property of Haleon- Confidential

[figure not shown]
May not be used, divulged, published or otherwise disclosed without the consent of Haleon

CCI [REDACTED] Abbreviated Clinical Protocol Template v1.0

8 STATISTICAL CONSIDERATIONS AND DATA ANALYSES

8.1 Sample Size Determination

The primary objective for this study is to evaluate the over-time effects of Emergen-C Core Super Orange Powder on QoL parameters, as measured by the MFI domain scores (*General Fatigue, Physical Fatigue, Reduced Activity, Reduced Motivation, Mental Fatigue*), compared to placebo, when taken daily over 12 weeks.

A total of 300 subjects will be randomized (approximately 150 per group) to ensure sufficient power for the primary analysis. Assuming a maximum drop-out rate of 20%, approximately 240 evaluable subjects in total (120 per group) complete the entire study.

The sample size calculation was performed using R software version 4.4.1.

8.2 Populations for Analysis

8.2.1 Definitions of Analysis Populations

The following four study populations will be used for statistical analysis:

- The modified Intention-To-Treat (mITT) population consists of all subjects who have been randomized, completed baseline visit (visit 1), completed at least one-post baseline MFI domain assessment and have taken at least one dose of their allocated randomized product. Group allocation will be based on the study product to which the subject was randomized. All subjects who receive a randomization number will be considered randomized. The mITT population will be used as the primary population for the assessment of efficacy.
- The Per-Protocol (PP) population includes all mITT subjects who have adhered to the allocated treatment regime and are not considered to have been affected by protocol deviations.
- The Safety population (SP) includes all randomized subjects who have taken at least one dose of their randomized study product. Analyses of this population will be based on the investigational product received.

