8.3.4 Safety Analysis(es)

The absolute and relative frequency of AEs in each group will be reported, including the total number of events, the total number of patients experiencing at least one event, and the frequency of events by severity and AE category.

Safety analyses will be performed on the Safety population, according to investigational product received. AEs will be regarded as 'treatment emergent' if they occur on or after the first use of investigational product at Baseline (Visit 2). In the event of a missing start date, an AE will be assumed to be 'treatment emergent' unless the end date is prior to starting treatment. In case of misallocation compared to the randomization schedule, TEAEs will be associated with the most recent investigational product received.

AE will be assessed by the investigator or medically qualified designee. AE review and coding will be in line with the Site and Safety Management Plan.

A listing of all AEs will be presented for all subjects in the Safety population with the following AE summaries (number of distinct AEs and frequency/proportion of subjects affected) presented by treatment group and overall:

- TEAEs
- TEAEs by System Organ Class (SOC) and Preferred Term (PT)
- Treatment emergent treatment related AEs by SOC and PT
- Treatment emergent treatment related serious AEs by SOC and PT

Separate listings will be presented for:

- Deaths, SAEs and any AEs leading to product or study discontinuation.
- Exposure to study product

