5.1.3 Analysis Populations

Three analysis populations are defined.

Population	Definition / Criteria	Analyses Evaluated
Safety	
 • Comprise of all subjects who receive at least one dose of study product. • This population will be based on the treatment the subject actually received. 	
 • Safety
Modified Intent-To-Treat (mITT)	
 • Comprise of all randomized subjects with completed baseline visit (visit 1), at least one completed post-baseline MFI domain assessment, and taken at least one dose of allocated product. • This population will be based on the treatment to which the subject was randomized. 	
 • Demographics • Baseline Characteristics • Efficacy • Subgroup analyses

Population	Definition / Criteria	Analyses Evaluated
	
 Any subject who receives a randomization number will be considered to have been randomized. 	
Per-Protocol (PP)	
 Comprised of all subjects in the mITT population who have adhered to treatment regime and were not affected by protocol deviations. 	
 Sensitivity (Primary endpoint)

Note: Please refer to [Appendix 1](#): List of Data Displays which details the population to be used for each display being generated.

The numbers of subjects included in each of the analysis populations will be summarized (Table 14.1.1). Subjects excluded from any of the analysis populations will be listed in Listing 16.2.3.1, with the reason for exclusion.

The primary population for assessment of efficacy will be the mITT Population. A PP analysis will be performed for efficacy analysis of the primary endpoint if at least 10% of the mITT subjects are excluded from the PP Population. Efficacy data determined to have been potentially impacted by a protocol deviation will be excluded from the PP analysis. A decision on whether a protocol deviation impacts efficacy data and whether to perform a PP analysis will be made at the BDRM.

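### The mITT entry rule requires a dose of the allocated product, so a subject who took only the other arm's product is excluded from the primary efficacy population despite the as-randomised rule

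*Protocol*

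**What the plan says.** Protocol 8.2.1 builds the mITT population, the primary population for efficacy, from randomised subjects who completed the baseline visit, gave at least one post-baseline MFI domain assessment and "have taken at least one dose of their allocated randomized product". It then states: "Group allocation will be based on the study product to which the subject was randomized".

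SAP 5.1.3 has the same pair of rules. Entry requires a subject to have "taken at least one dose of allocated product", and "This population will be based on the treatment to which the subject was randomized".

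The plan foresees that a subject may receive the wrong product, but gives a rule only for safety. Protocol 8.3.4 says: "In case of misallocation compared to the randomization schedule, TEAEs will be associated with the most recent investigational product received". SAP 5.7.1 repeats this. SAP 5.3 lists planned and actual product for every randomised subject.

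The Safety definitions differ. Protocol 8.2.1 requires at least one dose of the subject's randomised product, yet analyses by product received. SAP 5.1.3 requires a dose of study product, without saying which, and also analyses by product received.

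Protocol 8.2.2 settles exclusions at a blinded review before database lock. SAP 3.2 releases the randomisation codes only after lock.

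**The concern.** An as-randomised rule does its main work when the product taken differs from the product assigned. Here the entry condition acts first. A subject who took nothing but the other arm's product has no dose of the allocated product, so is removed before the as-randomised sentence can apply. That is a post-randomisation exclusion based on the product received, in the population that carries the primary test.

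There is also a practical problem. Whether a dose was of the allocated product depends on the treatment codes, and the people deciding population membership do not have them.

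What is at stake is the consistency of the primary population with the principle that both documents state for it. It is not a demonstrated error in the treatment estimate.

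**Working it through.** **Step 1. Apply the definitions to each possible subject.** Assume the other mITT conditions are met.

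| Product taken | mITT, protocol and SAP | Safety, protocol | Safety, SAP |
|---|---|---|---|
| Allocated product only | in, as randomised | in | in |
| Both products, at least one allocated dose | in, as randomised | in, by product received | in, by product received |
| Other arm's product only | **out** | **out** | in, by product received |
| No dose | out | out | out |

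Only the third row is in conflict. For mITT it contradicts the as-randomised sentence. For Safety the protocol and SAP disagree, and the protocol's version removes a subject to whom its own misallocation rule in 8.3.4 is addressed.

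**Step 2. Can the criterion be applied blind?** Protocol 7.3 keeps the study statisticians, data managers and investigator staff blinded, marks cartons with a kit number and uses no product codes. A blinded reviewer could at most see that a subject had a kit other than the one assigned. The reviewer could not tell whether that kit held the same product or the other one. A criterion of any study product needs only the diary.

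**Step 3. Reproduce the plan's power figure.** Inputs from Protocol 4.1: 120 evaluable subjects per group, difference 0.5 SD, two-sided alpha 1% (0.05/5 = 0.01), stated power over 90%.

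- Normal approximation: Φ(0.5 × √(120/2) − 2.576) = Φ(3.873 − 2.576) = 90.3%.
- Exact non-central t, 238 degrees of freedom: 89.8%.

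The stated figure is reproduced to within rounding and method. The point does not depend on it; it is the base for step 4.

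**Step 4. Illustrate the effect of dropping against keeping.** The documents give no wrong-product rate. Assume a share m of each arm took only the other product and responds fully to it.

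- Dropped, as the text literally requires: n = 120 × (1 − m) per arm, effect 0.5 SD.
- Kept as randomised: n = 120 per arm, difference = 0.5 × (1 − 2m), within-arm SD = √(1 + 0.25 × m(1 − m)).

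| m (assumed) | Subjects of 300 | Power if dropped | Difference if kept | Power if kept |
|---|---|---|---|---|
| 0 | 0 | 89.8% | 0.50 | 89.8% |
| 1% | 3 | 89.4% | 0.49 | 88.3% |
| 2% | 6 | 89.1% | 0.48 | 86.6% |
| 5% | 15 | 87.9% | 0.45 | 80.7% |

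Dropping costs 0.4 to 1.9 points (89.8 − 89.4; 89.8 − 87.9). Keeping costs 1.5 to 9.1 points (89.8 − 88.3; 89.8 − 80.7). The literal rule therefore gives the less diluted comparison.

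**The case against.** The strongest reply is that this is drafting, not design. The authors probably meant only that a subject had been dosed. A shipping error under a double blind, with identical unmarked sachets, has no stated link to arm or outcome, so dropping such subjects need not bias anything, and on the figures above it costs less power than keeping them. Exclusions are listed with reasons (SAP 5.1.3), as are planned and actual product (SAP 5.3). All of this stands. It limits the size of the point, but does not remove the contradiction between the entry condition and the as-randomised sentence.

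A reader might infer more in two ways, and neither is supported.

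- **That anyone sent a wrong kit is dropped.** The condition concerns doses taken, and one dose of the allocated product is enough. A subject with mixed exposure stays in and is analysed as randomised.
- **That lost parcels are replaced by the next kit in line, whatever its arm.** Protocol 5.4 says only that the "study team will discuss with participant and arrange a new shipment if needed", and Protocol 7.3 says "Study products will be dispensed in sequential order as per the randomization schedule". Neither says that a replacement is the next kit in sequence. Section 7.3 also says that each subject uses only one of the two products and that the carton holds only the product to which the subject was randomised. How a matching replacement is chosen is not described, but Protocol 7.2 and 7.3 refer to further supply instructions and randomisation directions that are not part of these documents. No count of affected subjects can be built on this route.

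**Conclusion.** The point holds in a narrow form. In both documents the mITT entry condition excludes a randomised subject who took only the other arm's product. This contradicts the as-randomised rule in the same definition and cannot be fully decided at a blinded review. Subjects with at least one allocated dose are not affected.

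The number affected is unknown, probably very small and possibly zero. No bias of a given size is shown. The 1–5% range in the working is an assumption made to show direction, and it also assumes full response to the product taken. The objection is departure from the stated principle, not loss of power. This is a minor but worthwhile correction.

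**What to change.** In Protocol 8.2.1 and SAP 5.1.3, change the mITT dosing criterion to *at least one dose of any study product*, with subjects analysed as randomised. In Protocol 8.2.1, change the Safety criterion from the subject's randomised product to study product, analysed by product received, so that it agrees with the SAP and with the misallocation rule in 8.3.4.

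The cost is one phrase in the SAP and two in the protocol, with no new data. The downside is that any wrong-product subjects kept as randomised slightly dilute the estimated effect. The per-protocol population, which requires adherence to the allocated regimen, remains the place to leave them out.

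SAP Appendix 2 shows that a blinded data review has already taken place. If the codes have since been released, the alternative is to report how many subjects took only the other product, using the planned and actual product in Listing 16.1.7.1. If there are any, show the primary result with them included as randomised.
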